What is the analgesic effect of peribulbar anesthesia compared to topical anesthesia in patients with diabetic retinopathy undergoing PRP with argon laser?

Objectives and hypotheses

General objective

To determine the reduction in the NRS scale between eyes of patients undergoing PRP following an injection of peribulbar anesthesia with 2% lidocaine + 0.5% bupivacaine versus those eyes receiving a sham injection.

Specific objectives

- To determine the pain score using the NRS scale between the eyes of patients undergoing PRP following the application of a sham injection vs transeptal anesthesia with 2% lidocaine + 0.5% bupivacaine.
- To measure and compare the frequency of adverse effects and complications associated with the transeptal anesthesia intervention versus those of patients receiving a sham injection.
- To measure heart rate before and after the application of panretinal photocoagulation.
- To measure respiratory rate before and after the application of panretinal photocoagulation.

-
- To measure systolic and diastolic blood pressure pre- and post-application of panretinal photocoagulation.
- To measure oxygen saturation pre- and post-application of panretinal photocoagulation.

General hypothesis

In patients who received panretinal photocoagulation, eyes undergoing peribulbar anesthesia will present a lower pain score on the NRS scale than eyes that received a sham injection.

Specific hypotheses

- In patients who received panretinal photocoagulation, eyes undergoing peribulbar anesthesia will present a pain score on the NRS scale 20% lower than eyes that only received a sham injection.
- The incidence of adverse effects and complications of peribulbar anesthesia is similar to that of the sham injection.
- In eyes undergoing intervention with prior peribulbar anesthesia, the post-procedure increase in heart rate will be 10% lower than the increase observed in eyes receiving a sham injection.
- In eyes undergoing intervention with prior peribulbar anesthesia, the post-procedure increase in respiratory rate will be 10% lower than the increase observed in eyes receiving a sham injection.

- In eyes undergoing intervention with prior peribulbar anesthesia, the post-procedure increase in systolic and diastolic blood pressure will be 10% lower than the increase observed in eyes receiving a sham injection.

Methods

Study design

Prospective, randomized, single-masked, controlled trial

Patients

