Patients were recruited from the Asociación Para Evitar la Ceguera en México, I.A.P. Retina department according to specific eligibility criteria. Adults aged 18 years or older with proliferative diabetic retinopathy who were scheduled to undergo their first PRP session and were able to maintain the required posture at the slit lamp throughout the procedure were included. Exclusion criteria were a history of phobic anxiety disorder related to needles or injections; known allergies or hypersensitivity to lidocaine, bupivacaine, or tetracaine; use of analgesics within 24 hours prior to treatment; and cognitive or motor impairments that could hinder effective communication of pain.

Study design

A block randomization scheme was created to ensure a balanced allocation of the eyes across the study groups. Eleven blocks containing four possible permutations for the two groups were created. The intervention group received peribulbar anesthesia and the control group received topical anesthesia. The blocks were numbered randomly from one to 11, and one eye of each participant was assigned to the treatment or control group according to the permutation, with the contralateral eye assigned to the corresponding alternative.

The eyes assigned to the treatment group received a single drop of topical 5% tetracaine to improve patient comfort during the peribulbar injection, followed by a two-minute observation period. A mixture of 1.5 mL of 0.5% bupivacaine and 1.5 mL of 2% lidocaine was prepared in a 3 mL syringe. The peribulbar injection was administered using a 25G needle inserted horizontally through the inferior palpebral conjunctiva, directed axially over the infraorbital rim, and then angled upward to deliver the anesthetic into the orbit.

After a five-minute latency period, the eyes assigned to the control group, which also received 5% tetracaine, were administered a sham injection. In this group, topical 5% tetracaine was applied, followed by a two-minute observation period. The sham injection consisted of a 3 mL syringe filled with normal saline, without a needle, used to simulate insertion by applying pressure at the same site as the peribulbar injection.

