Five minutes after the sham injection, the participants underwent PRP using a double-frequency Nd:YAG 532-nm laser (PUREPOINT®, ALCON) following the standard PRP protocol, starting with the right eye. Each eye received between 1,200 and 1,500 burns, with sizes ranging from 200 μ m to 500 μ m. Pulse durations were set between 100-200 ms. The power was titrated before initiating treatment to obtain a gray-whitish burn, and adjusted throughout the procedure in order to avoid under- or over-treatment. A period of 10 minutes was provided between the right- and left-eye PRP sessions.

Variables and Measurements

The primary variable assessed in this study was patient perception of pain during PRP administration in each eye, measured using the numerical rating scale (NRS). The Initiative on Methods, Measurement, and Pain Assessment in Clinical Trials (IMMPACT) recommends the use of this scale due to its simplicity, patient preference, and high completion rates, especially among elderly individuals. The NRS measures pain intensity on a scale of 0 to 10, where 0 corresponds to the absence of pain and 10 represents the

worst pain imaginable.²⁴ The evaluator administering the NRS was not masked to the treatment allocation. The secondary variables assessed in this study were heart rate, respiratory rate, oxygen saturation (SpO₂), and blood pressure measured before and after the application of PRP in each eye. All vital signs were measured with the Aquarius Vital Sign Monitor (Shenzhen Northern Meditec Limited, Shenzhen, China) at baseline before the start of PRP, and at the 1-, 5-, 10-, and 15-minute marks while undergoing PRP application in each eye.

Safety was evaluated by monitoring for ocular and non-ocular adverse events, assessing extraocular movements after peribulbar injection, and conducting a 45-minute observation period after the PRP session.

Standardized methods

A) Topical anesthesia with 0.5% Tetracaine

1. Patient seated in a comfortable position.
2. 1 drop of 0.5% tetracaine will be applied onto the ocular surface to be treated and the conjunctival fornices.
3. Any excess residue will be cleaned with a cotton swab.

B) Peribulbar injection of 3 mL of 2% lidocaine + 0.5% bupivacaine

1. Patient in a comfortable position.
2. 2 drops of 0.5% tetracaine will be applied to the conjunctival fornices 10 minutes prior to the administration of anesthesia.

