3. A Mixture of 1.5 mL of 2% lidocaine and 1.5 mL of 0.5% bupivacaine will be prepared in a 5 mL syringe.
4. Lower eyelid skin will be cleaned with 97% alcohol.

5. Palpation of the orbital notch with the index finger or thumb, located at the junction of the outer 1/3 and the inner 2/3 of the orbital rim.
6. The patient will be asked to look upward (supraversion).
7. Using a 5 mL syringe, a 25G needle will be inserted, bevel up, through the skin, entering near the bony margin, lateral to the notch.
8. Aspiration prior to injecting the medication will be performed.
9. 3 mL of 2% lidocaine + 0.5% bupivacaine will be injected
10. Extraocular movements will be evaluated.

Sham peribulbar injection

1. Patient in a comfortable position.
2. 2 drops of 0.5% tetracaine will be applied to the conjunctival fornices 10 minutes prior to the administration of anesthesia.
3. Lower eyelid skin will be cleaned with 97% alcohol.
4. Palpation of the orbital notch with the index finger or thumb, located at the junction of the outer 1/3 and the inner 2/3 of the orbital rim.
5. With a 5 ml syringe filled with normal saline without a needle, a peribulbar injection will be simulated near the bony margin, lateral to the notch.
6. Extraocular movements will be evaluated.

Statistical Analysis Plan

The sample size was calculated using a two-sample t-test to compare two means, based on previous results reported by Zakrzewski et al.³¹ Assuming an alpha risk of 0.05 and a beta risk of 0.2, a minimum of 44 patients was required to find statistically significant differences. The Shapiro-Wilk test was used to assess normality. Descriptive statistics were used to analyze the baseline population characteristics. Data from normally distributed variables is

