presented as mean (SD), and data from non-normally distributed variables as median (IQR). The grouped quantitative variables had a normal distribution; however, when the treatment groups were separated, all the variables had a non-normal distribution. Repeated measurements of related groups with a non-normal distribution were analyzed using the Friedman test. Group comparisons of unrelated groups with a non-normal distribution were performed using the Mann-Whitney U test. The measurements of vital signs, NRS score, and laser parameters were registered into a coded Excel spreadsheet (Microsoft Corporation), and statistical analysis was performed using SPSS software (version 29.0, IBM, Chicago, IL, USA). A p-value of < 0.05 was considered statistically significant.

References

6. GBD 2019 Blindness and Vision Impairment Collaborators. Causes of blindness and vision impairment in 2020 and trends over 30 years, and prevalence of avoidable blindness in relation to VISION 2020: the Right to Sight: an analysis for the Global Burden of Disease Study. *Lancet Glob Health.* 2021;9(2):e144-e160. doi:10.1016/S2214-109X(20)30489-7

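### Each patient's two eyes form a matched pair, but the SAP ties no test to the primary NRS outcome, and its only group-comparison test assumes unrelated groups

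*Combined protocol and SAP*

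**What the plan says.** In the Combined protocol and SAP, Methods, Study design, one eye of each participant is allocated to a group, "with the contralateral eye assigned to the corresponding alternative". Under Variables and Measurements, the primary outcome is a 0 to 10 NRS pain rating taken for each eye. Each patient therefore supplies one rating under each treatment.

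The Statistical Analysis Plan names two inferential tests for non-normal data:

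- For related data: "Repeated measurements of related groups with a non-normal distribution were analyzed using the Friedman test".
- For comparing groups: "Group comparisons of unrelated groups with a non-normal distribution were performed using the Mann-Whitney U test".

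Neither sentence mentions the NRS. No signed-rank test, paired t-test or mixed model appears. Rank tests are justified by the distribution within each arm: "when the treatment groups were separated, all the variables had a non-normal distribution". The sample size is also unpaired: "The sample size was calculated using a two-sample t-test to compare two means".

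The general objective is to determine the reduction in NRS between the two kinds of eye. One specific hypothesis is that peribulbar eyes "will present a pain score on the NRS scale 20% lower than eyes that only received a sham injection". The SAP provides for means or medians and a p-value threshold of 0.05, with no confidence interval.

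**The concern.** The documents describe no unrelated groups, so a test for unrelated groups does not fit the design. Two ratings from one person share that person's pain threshold, anxiety and use of the scale, and would usually be positively correlated. An independent-samples test takes the variance of the treatment difference to be larger than it is, so its p-value is too large.

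Three further things follow:

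- The result that the general objective asks for, a within-patient reduction with its uncertainty, is not planned.
- Checking normality arm by arm looks at the wrong quantity. For pairs, what matters is the distribution of the within-patient differences.
- The secondary comparisons have the same gap. Friedman across time within one arm does not compare arms, and Mann-Whitney between arms would again drop the pairing.

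**Working it through.** **The plan's own figure.** The SAP states: "Assuming an alpha risk of 0.05 and a beta risk of 0.2, a minimum of 44 patients was required to find statistically significant differences". It gives no mean difference or SD, so 44 cannot be reproduced. It can be inverted to find the standardised effect d that it implies (two-sided test assumed, since sidedness is not stated):

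d = (1.960 + 0.842) × √(2/n per group)

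- 44 per group: 2.802 × √(2/44) = 0.597 (0.604 by the exact t-test).
- 44 in total, 22 per group: 2.802 × √(2/22) = 0.845 (0.865 by the exact t-test).

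**Why the error rate moves.** With n pairs, common SD σ and between-eye correlation ρ, the mean difference has variance 2σ²(1 − ρ)/n. An unpaired test uses 2σ²/n. The effective critical value is then about 1.96/√(1 − ρ):

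- ρ = 0.3: 1.96/√0.7 = 2.34, two-sided error about 1.9%.
- ρ = 0.5: 1.96/√0.5 = 2.77, about 0.6%.
- ρ = 0.7: 1.96/√0.3 = 3.58, about 0.03%.

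**Simulation on an NRS-like scale.** Assumptions, none of them in the documents: 44 pairs, bivariate normal scores rounded and clipped to 0–10, sham-eye mean 5, SD 2.5, and the correlations shown. There were 8,000 runs per cell, or 10,000 for d = 0.865. The effect d = 0.40 is 1 point, or 20% of the assumed mean of 5 (1/2.5 = 0.40). Each cell gives the percentage of runs rejecting at nominal 5%, Mann-Whitney / signed-rank.

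| ρ | No effect | d = 0.40 | d = 0.604 | d = 0.865 |
|---|---|---|---|---|
| 0 | 5.3 / 5.2 | 42.9 / 42.4 | 76.9 / 76.7 | 97.2 / 96.9 |
| 0.3 | 2.1 / 4.5 | 42.4 / 56.3 | 80.8 / 89.3 | 98.8 / 99.5 |
| 0.5 | 0.7 / 5.3 | 41.7 / 70.4 | 84.6 / 96.6 | 99.6 / >99.9 |
| 0.7 | 0.1 / 5.0 | 39.6 / 89.1 | 90.1 / 99.8 | >99.9 / >99.9 |

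A separate run of the same model gave 0.8% for Mann-Whitney at ρ = 0.5 with no effect, which is the same within simulation error.

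Power lost by ignoring the pairing, for ρ = 0.3, 0.5 and 0.7:

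- d = 0.40: 13.9, 28.7 and 49.5 points.
- d = 0.604: 8.5, 12.0 and 9.7 points.
- d = 0.865: under 1 point throughout.

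If the correlation were negative, the direction would reverse: at ρ = −0.2 Mann-Whitney rejects 7.5% of the time with no effect.

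**Friedman on two eyes.** With two conditions per patient, Friedman reduces to a sign test. It is valid (type I error 4.6% to 5.5% for ρ from 0 to 0.8) but weaker than signed-rank: 79%, 91% and 99% at d = 0.604 for ρ = 0.3, 0.5 and 0.7.

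**The case against.** The best defence is that the SAP never says Mann-Whitney is used on the NRS. It does list Friedman for related groups, and Friedman on two eyes would be a valid paired test. This stands in part: the use of Mann-Whitney on the primary outcome is inferred. But the only serial measurements described are vital signs, at baseline and at 1, 5, 10 and 15 minutes, and Friedman most naturally belongs to those. The only sentence about comparing groups names Mann-Whitney, and the sample size is unpaired too. If the inference is wrong, the primary test is still unnamed, and the remedy is the same.

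The second defence concerns size. A reader might infer that the flaw makes a significant result untrustworthy. It does not: with positive correlation the error is conservative. A reader might also infer that most of the power is lost. The documents do not establish that, because they give no correlation, SD or mean difference. At the effects implied by 44, Mann-Whitney keeps at least about 80% power for correlations of 0.3 to 0.7. The large losses arise only at a smaller effect, such as a 20% reduction from an assumed mean of 5. This objection stands in full.

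Third, a reader might take 20% as a margin that the confidence interval must clear. The general hypothesis says only that the score will be lower, and 20% can equally be the anticipated effect. The documents do not settle which. What remains is narrower: a p-value against zero difference does not by itself show a 20% reduction.

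**Conclusion.** Wrong as written. The design is paired by patient, no test is tied to the primary NRS outcome, and the only group-comparison test given assumes independence. Applied to these eyes, it would run at about 2%, 0.8% or 0.1% instead of 5% for correlations of 0.3, 0.5 or 0.7. The cost in power ranges from none (zero correlation, or a large effect) through 8 to 12 points (d about 0.60) to 14 to 50 points (d = 0.40).

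These sizes rest on the assumed mean of 5, SD of 2.5, correlations and two-sided testing. The mismatch between design and test does not, nor does the absence of a paired estimate and interval. A significant result would not be undermined by this flaw; a non-significant one would be hard to interpret.

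**What to change.** - **Primary analysis.** Name it for the NRS: the within-patient difference, sham eye minus peribulbar eye, tested by Wilcoxon signed-rank with the Hodges-Lehmann estimate and 95% CI. A paired mean difference with 95% CI is an acceptable alternative. Fix the choice by design, not by Shapiro-Wilk on each arm.
- **20% hypothesis.** Report the percentage reduction with its 95% CI. Do not present p < 0.05 alone as showing a 20% reduction.
- **Laser parameters.** Compare them between eyes with paired methods.
- **Vital signs.** Use an analysis that keeps both the patient pairing and the repeated time points, for example a mixed model with patient and eye-within-patient effects, treatment and time.

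The cost is SAP wording and a re-run on the existing data. No new patients or measurements are needed.
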